6.1 Dose reduction for adverse events

Adult patients receiving 200 mg daily or pediatric patients receiving 130 mg/m² who require dose reduction for adverse events will have their dose reduced to 100 mg (or 65 mg/m²). A second dose reduction to 50 mg daily is allowed for patients on potent CYP3A4 inhibitors. Patients with impaired renal function receiving 100mg daily who require a dose reduction for adverse events will have their dose reduced to 50mg daily. Treatment and dose reductions will be based on eGFR and not on serum creatinine for patients with moderate renal dysfunction.

Dose Modification Table for Non-hematologic and Hematologic Toxicities

Adverse Event	CTCAE 4.0 Grade/Attribution	Protocol Action
Non-hematologic toxicity (LFTs and eGFR [^] excluded)	Grade 2 >7 days that is probably or definitely related to imatinib.	Hold study drug; *If toxicity resolves to \leq grade 1 or baseline within 14 day days: restart drug at same dose level.
Non-hematologic toxicity (LFTs and eGFR [^] excluded)	Same grade 2 recurs that is probably or definitely related to imatinib.	Hold study drug; *If toxicity resolves to \leq grade 1 or baseline within 14 day days: decrease dose by 1 dose level. **If toxicity does NOT resolve to \leq Grade 1 or baseline within 14 day days: patient comes off study.
Non-hematologic toxicity (LFTs and eGFR [^] excluded)	Same grade 2 recurs after dose reduction that is probably or definitely related to imatinib.	Patient comes off study. Exception: patients on a CYP3A4 inhibitor [which allows a second dose reduction].

Adverse Event	CTCAE 4.0 Grade/Attribution	Protocol Action
Non-hematologic toxicity (LFTs and eGFR [^] excluded)	Grade 3 that is probably or definitely related to imatinib.	Hold study drug; *If toxicity resolves to \leq grade 1 or baseline within 14 day days: decrease dose by 1 dose level. **If toxicity persists >14 days or if Grade 3 recurs after dose reduction: patient comes off study.
Non-hematologic toxicity (LFTs and eGFR [^] excluded)	Grade 4 that is probably or definitely related to imatinib.	Patient comes off study
Non-hematologic toxicity: LFTs ; eGFR [^]	Grade 2	No dose adjustment.
Non-hematologic toxicity: LFTs; eGFR [^]	Grade 3 >7 days that is probably or definitely related to imatinib.	Hold study drug; *If toxicity resolves to baseline within 14 day days: restart drug at same dose level.

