Non-hematologic toxicity: LFTs; eGFR [^]	Same grade 3 recurs that is probably or definitely related to imatinib.	Hold study drug; *If toxicity resolves to baseline within 14 day days: decrease dose by 1 dose level. **If toxicity does NOT resolve to baseline within 14 day days: patient comes off study.
Non-hematologic toxicity: LFTs; eGFR [^]	Grade 4 that is probably or definitely related to imatinib.	Patient comes off study
Hematologic: Cytopenias	Grade 2	No dose adjustment.
Hematologic: Neutrophil or Platelet toxicity	Grade 3 on two sequential evaluations within 7 days that is probably or definitely related to imatinib.	Hold study drug; *Until counts recover to a grade 2 then restart at same dose level.

Adverse Event	CTCAE 4.0 Grade/Attribution	Protocol Action
Hematologic: Neutrophil or Platelet toxicity	Same grade 3 recurs that is probably or definitely related to imatinib.	Hold study drug; *Until counts recover to a grade 2 then decrease dose by 1 dose level.
Hematologic: Neutrophil or Platelet toxicity	Same grade 3 recurs after dose reduction that is probably or definitely related to imatinib.	Patient comes off tudy.
Hematologic: Neutrophil or Platelet toxicity	Grade 4	*If toxicity resolves to < Grade 2 within 14 day days: Decrease dose by 1 dose level. **If toxicity does NOT resolve to < grade2 within 14 day days: Patient comes off study.
Hematologic: Neutrophil or Platelet toxicity	Same grade 4 recurs	Patient comes off study.

^ = **Patients with moderate renal dysfunction.** Patient with mild renal dysfunction or normal renal function at baseline will receive dose adjustment based on the standard guidelines for other non-hematologic provided in Table 1.

Exceptions to the above treatment modifications:

1. Alopecia.
2. Grade 2 or 3 low electrolyte levels in patients with chronic low levels of the same electrolyte. Such individuals should receive supplementation and any worsening of levels should be discussed with the PI to determine whether to consider dose limiting.
3. Hypocalcemia toxicity grade should be assigned based on the calcium level corrected for degree of hypoalbuminemia according to the following formula: albumin ↓ 1 gram/dL: total calcium ↑ 0.2 mmol/L. Ionized calcium can also be used to assess toxicity.
4. Grade 3 fever.
5. Infection or neutropenic fever unless attributed to imatinib mesylate.
6. Lymphopenia any grade
7. Grade 3 hypertriglyceridemia or hypercholesterolemia.

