8. Grade 3 non-life-threatening basal or squamous cell carcinoma of the skin. This patient population is predisposed to non-melanoma skin cancer due to chronic immunosuppression associated with cGVHD treatment.
9. Grade 2 fatigue

10. Grade 2 dry skin
11. Grade 2 albumin
12. Grade 2 or 3 asymptomatic CPK elevation with no evidence of rhabdomyolysis or cardiac myositis.
13. Grade 2 proteinuria
14. Grade 2 tinnitus
15. Grade 2 insomnia
16. Grade 2 rash
17. Grade 2 anorexia

Each treatment cycle should be no longer than 28 days. Doses withheld while recovering from toxicity should not be made up.

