8.3.3 Protocol-Specific Expedited Adverse Event Reporting Exclusions

For this protocol only, certain AEs/grades are exceptions to the Expedited Reporting Guidelines and do not require expedited reporting (i.e., CTEP-AERS). The following AEs must be reported through the routine reporting mechanism (Section 7.4):

CTCAE Category	Adverse Event	Grade	Hospitalization/ Prolongation of Hospitalization	Attribution	Comments
Dermatology/skin	Alopecia	2	N/A	Yes or no	
Constitutional	Fever	3	No	no	
Infection	Febrile neutropenia	3		no	
Infection	Infection	2	No	no	
Blood/Bone Marrow	Lymphopenia	Any	No	Yes or no	
Metabolic/Laboratory	Hyperlipidemia	2,3	N/A	Yes or no	
Metabolic/Laboratory	Hypercholesterolemia	2,3	N/A	Yes or no	
Metabolic/Laboratory	Electrolyte abnormality	2,3	N/A	Yes or no	Patient with chronic low levels may be supplemented. Discuss with PI/LAI to see if dose limiting.
Secondary Malignancy	Non-life threatening basal or squamous cell skin carcinoma	3	No	Yes or no	This patient population is predisposed to non-melanoma skin cancer due to chronic immunosuppression associated with cGVHD treatment.
Constitutional	Fatigue	2	N/A	Yes or no	
Dermatology/skin	Dry Skin	2	N/A	Yes or no	

Metabolic/Laboratory	Albumin	2	N/A	Yes or no	
Metabolic/Laboratory	CPK	2,3	N/A	Yes or no	Asymptomatic CPK elevation with no evidence of rhabdomyolysis or cardiac myositis.
Metabolic/Laboratory	Proteinuria	2	N/A	Yes or no	
Auditory/Ear	Tinnitus	2	N/A	Yes or no	
Constitutional	Insomnia	2	N/A	Yes or no	
Dermatology/skin	Rash	2	N/A	Yes or no	
Gastrointestinal	Anorexia	2	N/A	Yes or no	

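### Section 6.1, exception 7 exempts lipid elevations at grade 3 only, so the dosing rule acts on prolonged related grade 2 events but not on grade 3

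*Combined protocol and SAP*

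**What the plan says.** The table in section 6.1 covers all non-hematologic toxicity except LFTs and, for patients with moderate renal dysfunction, eGFR. Its rows, for events with probable or definite attribution, are:

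- "Grade 2 >7 days that is probably or definitely related to imatinib": hold; restart at the same dose if the event resolves within 14 days.
- "Same grade 2 recurs that is probably or definitely related to imatinib": hold; go down one dose level if it resolves within 14 days, otherwise off study. A further recurrence after reduction also means off study, except for patients on a CYP3A4 inhibitor.
- "Grade 3 that is probably or definitely related to imatinib": hold; go down one dose level if it resolves within 14 days. Off study if it persists beyond that or recurs after reduction.
- Grade 4: off study.

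A list of 17 exceptions follows. Item 7 reads "Grade 3 hypertriglyceridemia or hypercholesterolemia". No other item mentions lipids. Elsewhere the list spells out a range where it means one: item 2 is "Grade 2 or 3 low electrolyte levels in patients with chronic low levels of the same electrolyte", item 12 is "Grade 2 or 3 asymptomatic CPK elevation with no evidence of rhabdomyolysis or cardiac myositis", and item 6 is "Lymphopenia any grade".

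Section 8.3.3 has a similar list for a different purpose, stating that "certain AEs/grades are exceptions to the Expedited Reporting Guidelines and do not require expedited reporting". There, hyperlipidemia and hypercholesterolemia are both entered at grades 2 and 3.

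**The concern.** A dose modification rule should act at least as strongly on a worse grade as on a milder one. For lipids, item 7 removes the table action at grade 3 and leaves grade 2 under it, so the order is reversed.

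A site following the text would hold drug for a prolonged related grade 2 elevation, and could reduce the dose or remove the patient if it recurred. The same site would take no table action at grade 3. Tolerability of 200 mg is a primary objective, judged in section 14.1.1 by whether 8 or more of the first 10 patients tolerate the dose, so an unintended hold, reduction or removal is undesirable. If the site instead used common sense and treated grade 2 as exempt, it would depart from the approved protocol. Section 7.1.8 defines that as a deviation, and section 7.2.1 requires deviations to be reported to the IRB.

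**Working it through.** The documents give no figure to reproduce. The check applies the rule by grade and then compares the two lists.

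**Step 1. Apply section 6.1 to a lipid event of probable or definite attribution.**

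| Grade | Table action | Item 7 applies? | Action as written | Action if item 7 covered grades 2 and 3 |
|---|---|---|---|---|
| 2, more than 7 days | Hold; escalate on recurrence | No | Hold; escalate on recurrence | None |
| 3 | Hold, then reduce or off study | Yes | None | None |
| 4 | Off study | No | Off study | Off study |

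As written, the sequence is hold, none, off study, which does not rise with grade. With both grades exempt it is none, none, off study, which does.

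**Step 2. Could item 7 mean up to grade 3?** If naming grade 3 implied the lower grades, naming grade 2 as well in items 2 and 12 would be redundant. The list's own usage argues against that reading.

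**Step 3. Compare grades in 6.1 and 8.3.3.** Items 1, 3 and 5 of 6.1 state no grade, which leaves 17 − 3 = 14.

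| 6.1 item(s) | Event | Grade in 6.1 | Grade in 8.3.3 | Match |
|---|---|---|---|---|
| 2 | Low electrolytes | 2 or 3 | 2,3 | Yes |
| 4 | Fever | 3 | 3 | Yes |
| 6 | Lymphopenia | Any | Any | Yes |
| 7 | Lipids | 3 | 2,3 | **No** |
| 8 | Basal or squamous skin carcinoma | 3 | 3 | Yes |
| 9, 10, 11, 13, 14, 15, 16, 17 | Fatigue, dry skin, albumin, proteinuria, tinnitus, insomnia, rash, anorexia | 2 | 2 | Yes (8 items) |
| 12 | CPK | 2 or 3 | 2,3 | Yes |

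Matches: 1 + 1 + 1 + 1 + 8 + 1 = 13. Mismatches: 1, which is item 7.

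**Step 4. How often could it matter?** A hold at grade 2 needs all of the following:

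- A lipid value is obtained. Lipids are not itemised in the on-study laboratory list in 11.1.2, and Appendix B names only a 20-test chemistry panel without its contents.
- The value qualifies as an adverse event under 7.1.1.
- It stays at grade 2 for more than 7 days.
- Attribution is probable or definite. Lipids are not in the CAEPR in 8.1.

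Even then, a first event that resolves within 14 days restarts at the same dose, and section 6 requires discussion of every modification with the PI or LAI. The documents give no rate for such events, so no probability is calculated.

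**The case against.** The strongest objection is selectivity. Items 4 (fever) and 8 (skin carcinoma) also name grade 3 alone, so three items share the form. If it can be intended for fever, or is a drafting habit meaning even at grade 3, item 7 is not uniquely wrong. What singles lipids out is 8.3.3, and that list has its own reason to name grade 2. Under 8.3.2 an unexpected grade 2 event with at least possible attribution needs a 10-day report. Because lipids are absent from the CAEPR, grade 2 has to be listed to be excluded.

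Nor are the two lists mirror images. Alopecia and infection carry grades only in 8.3.3. Fever is excluded there only when unattributed and without hospitalization. The lipid terms also differ (hypertriglyceridemia in one, hyperlipidemia in the other).

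Much of this stands, and it weakens the inference about intent. It does not explain 8.3.3 fully: fatigue and anorexia are listed there at grade 2 although the SPEER already excepts both up to grade 3. For items 4 and 8 the two lists agree, and acting on more than 7 days of drug-related grade 2 fever may well be intended, so neither is claimed as an error.

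The objection also says that nothing of consequence follows. Grade 3 is indeed not left unguarded: unacceptable adverse events remain a reason to stop under 5.3, and unresolved attributable grade 3 toxicity counts toward the stopping rule in 14.1. These points limit the impact, but they neither supply a grade 2 lipid exemption nor put the written actions in a sensible order.

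**Conclusion.** The point holds and is minor. One of 17 exception items is affected, and it is the only one of the 14 graded items whose grade differs from 8.3.3. Confidence is high that the literal rule acts at grade 2 and not at grade 3. That grade 2 was omitted by mistake is an inference from the wording of items 2 and 12 and from the comparison with 8.3.3. The investigators could instead say that action at grade 2 is wanted, but then the grade 3 exemption would make no sense.

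The expected effect on dosing is very small. No effect on the 8-of-10 tolerability rule, the power or the efficacy analysis is shown. This is an inconsistency in an operative dosing rule, not a statistical error.

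**What to change.** Reword item 7 in section 6.1 to exempt hypertriglyceridemia or hypercholesterolemia at grade 2 or 3, in line with items 2 and 12 and the lipid rows of 8.3.3. If the investigators do want action at grade 2, delete item 7 so that the table applies at both grades. Leave item 4 (fever) as it is; at most, ask the investigators to confirm that grade 3 alone is intended.

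The cost is one list item in an amendment, with no new data.

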6.2 Dose adjustment for patients starting CYP3A4 inducers

Patients on inducers will start at a 50% higher dose as stated in sections 5.1 and 5.2.4.1.

7 SAFETY REPORTING REQUIREMENTS/DATA AND SAFETY MONITORING PLAN

7.1 Definitions

7.1.1 Adverse Event

An adverse event is defined as any reaction, side effect, or untoward event that occurs during the course of the clinical trial associated with the use of a drug in humans, whether or not the event is considered related to the treatment or clinically significant. For this study, AEs will include events reported by the patient, as well as clinically significant abnormal findings on physical examination or laboratory evaluation. A new illness, symptom, sign or clinically significant laboratory abnormality or worsening of a pre-existing condition or abnormality is considered an AE.

All AEs, including clinically significant abnormal findings on laboratory evaluations, regardless of severity, will be followed until satisfactory resolution. AEs should be reported up to 30 days following the last dose of study drug.

An abnormal laboratory value will be considered an AE if the laboratory abnormality is characterized by any of the following:

- Results in discontinuation from the study
- Is associated with clinical signs or symptoms
- Requires treatment or any other therapeutic intervention
- Is associated with death or another serious adverse event, including hospitalization.
- Is judged by the Investigator to be of significant clinical impact
- If any abnormal laboratory result is considered clinically significant, the investigator will provide details about the action taken with respect to the test drug and about the patient's outcome.

7.1.2 Suspected adverse reaction

Suspected adverse reaction means any adverse event for which there is a reasonable possibility that the drug caused the adverse event. For the purposes of IND safety reporting, 'reasonable possibility' means there is evidence to suggest a causal relationship between the drug and the adverse event. A suspected adverse reaction implies a lesser degree of certainty about causality than adverse reaction, which means any adverse event caused by a drug.

7.1.3 Unexpected adverse reaction

An adverse event or suspected adverse reaction is considered "unexpected" if it is not listed in the investigator brochure or is not listed at the specificity or severity that has been observed; or, if an investigator brochure is not required or available, is not consistent with the risk information described in the general investigational plan or elsewhere in the current application.

"Unexpected", also refers to adverse events or suspected adverse reactions that are mentioned in the investigator brochure as occurring with a class of drugs or as anticipated from the pharmacological properties of the drug, but are not specifically mentioned as occurring with the particular drug under investigation.

7.1.4 Serious

An Unanticipated Problem or Protocol Deviation is serious if it meets the definition of a Serious Adverse Event or if it compromises the safety, welfare or rights of subjects or others.

7.1.5 Serious Adverse Event

An adverse event or suspected adverse reaction is considered serious if in the view of the investigator or the sponsor, it results in any of the following:

- Death,
- A life-threatening adverse drug experience
- Inpatient hospitalization or prolongation of existing hospitalization
- Persistent or significant incapacity or substantial disruption of the ability to conduct normal life functions
- A congenital anomaly/birth defect.
- Important medical events that may not result in death, be life-threatening, or require hospitalization may be considered a serious adverse drug experience when, based upon appropriate medical judgment, they may jeopardize the patient or subject and may require medical or surgical intervention to prevent one of the outcomes listed in this definition.

7.1.6 Disability

A substantial disruption of a person's ability to conduct normal life functions.

7.1.7 Life-threatening adverse drug experience

Any adverse event or suspected adverse reaction that places the patient or subject, in the view of the investigator or sponsor, at immediate risk of death from the reaction as it occurred, i.e., it does not include a reaction that had it occurred in a more severe form, might have caused death.

7.1.8 Protocol Deviation (NIH Definition)

A protocol deviation is any change, divergence, or departure from the IRB approved research protocol.

7.1.9 Non-compliance (NIH Definition)

The failure to comply with applicable NIH Human Research Protections Program (HRPP) policies, IRB requirements, or regulatory requirements for the protection of human research subjects.

7.1.10 Unanticipated Problem

Any incident, experience, or outcome that:

- Is unexpected in terms of nature, severity, or frequency in relation to
 - (a) the research risks that are described in the IRB-approved research protocol and informed consent document; Investigator's Brochure or other study documents, and
 - (b) the characteristics of the subject population being studied; **AND**
- Is related or possibly related to participation in the research; **AND**
- Suggests that research places subjects or others at a *greater risk of harm* (including physical, psychological, economic, or social harm) than was previously known or recognized.

7.2 NCI-IRB Reporting

7.2.1 NCI-IRB Expedited Reporting of Unanticipated Problems and Deaths

The Protocol PI will report to the NCI-IRB:

- All deaths, except deaths due to progressive disease
- All Protocol Deviations
- All Unanticipated Problems
- All serious non-compliance

Reports must be received by the NCI-IRB within 7 working days of PI awareness via iRIS.

7.2.2 NCI-IRB Requirements for PI Reporting at Continuing Review

The protocol PI will report to the NCI-IRB:

1. A summary of all protocol deviations in a tabular format to include the date the deviation occurred, a brief description of the deviation and any corrective action.
2. A summary of any instances of non-compliance
3. A tabular summary of the following adverse events:

Version date: 04/20/15

- All Grade 2 **unexpected** events that are possibly, probably or definitely related to the research;
- All Grade 3 and 4 events that are possibly, probably or definitely related to the research;
- All Grade 5 events regardless of attribution;
- All Serious Events regardless of attribution.

NOTE: Grade 1 events are not required to be reported.

7.2.3 NCI-IRB Reporting of IND Safety Reports

Only IND Safety Reports that meet the definition of an unanticipated problem will need to be reported to the NCI IRB.

7.3 Data and Safety Monitoring Plan

7.3.1 Principal Investigator/Research Team

The clinical research team will meet on a regular basis when patients are being actively treated on the trial to discuss each patient. Decisions about dose level enrollment and dose escalation if applicable will be made based on the toxicity data from prior patients.

All data will be collected in a timely manner and reviewed by the principal investigator or a lead associate investigator. Adverse events will be reported as required above. Any safety concerns, new information that might affect either the ethical and or scientific conduct of the trial, or protocol deviations will be immediately reported to the IRB using iRIS.

The principal investigator will review adverse event and response data on each patient to ensure safety and data accuracy. The principal investigator will personally conduct or supervise the investigation and provide appropriate delegation of responsibilities to other members of the research staff.

8 ADVERSE EVENTS: LIST AND REPORTING REQUIREMENTS

Adverse event (AE) monitoring and reporting is a routine part of every clinical trial. The following list of AEs (Section 8.1) and the characteristics of an observed AE (Section 8.2) will determine whether the event requires expedited (via CTEP-AERS) reporting **in addition** to routine reporting.

8.1 Comprehensive Adverse Events and Potential Risks list (CAEPR) for Imatinib Mesylate (STI571, NSC 716051)

The Comprehensive Adverse Event and Potential Risks list (CAEPR) provides a single list of reported and/or potential adverse events (AE) associated with an agent using a uniform presentation of events by body system. In addition to the comprehensive list, a subset, the

Specific Protocol Exceptions to Expedited Reporting (SPEER), appears in a separate column and is identified with bold and italicized text. This subset of AEs (SPEER) is a list of events that are protocol specific exceptions to expedited reporting to NCI via CTEP-AERS (except as noted below). Refer to the 'CTEP, NCI Guidelines: Adverse Event Reporting Requirements' http://ctep.cancer.gov/protocolDevelopment/electronic_applications/docs/aeguidelines.pdf for further clarification. *Frequency is provided based on 5169 patients.* Below is the CAEPR for imatinib mesylate (STI571).

NOTE: Report AEs on the SPEER **ONLY IF** they exceed the grade noted in parentheses next to the AE in the SPEER. If this CAEPR is part of a combination protocol using multiple investigational agents and has an AE listed on different SPEERs, use the lower of the grades to determine if expedited reporting is required.

Version 2.3, November 9, 2011¹

Adverse Events with Possible Relationship to Imatinib Mesylate (STI571) (CTCAE 4.0 Term) [n= 5169]			Specific Protocol Exceptions to Expedited Reporting (SPEER) (formerly known as ASAEL)
Likely (>20%)	Less Likely (<=20%)	Rare but Serious (<3%)	
BLOOD AND LYMPHATIC SYSTEM DISORDERS			
Anemia			Anemia (Gr 3)
CARDIAC DISORDERS			
		Left ventricular systolic dysfunction	
	Pericardial effusion		Pericardial effusion (Gr 2)
GASTROINTESTINAL DISORDERS			
Abdominal pain			Abdominal pain (Gr 3)
	Anal mucositis		Anal mucositis (Gr 2)
	Ascites		Ascites (Gr 2)
Diarrhea	Constipation		Constipation (Gr 3)
			Diarrhea (Gr 3)
	Dyspepsia		Dyspepsia (Gr 3)
	Flatulence		Flatulence (Gr 2)
	Gastrointestinal hemorrhage ²		Gastrointestinal hemorrhage² (Gr 3)
	Mucositis oral		Mucositis oral (Gr 2)
Nausea			Nausea (Gr 3)
	Rectal mucositis		Rectal mucositis (Gr 2)
	Small intestinal mucositis		Small intestinal mucositis (Gr 2)
Vomiting			Vomiting (Gr 3)
GENERAL DISORDERS AND ADMINISTRATION SITE CONDITIONS			
	Chills		
	Edema face		
Edema limbs			Edema limbs (Gr 2)
Fatigue			Fatigue (Gr 3)
	Fever		Fever (Gr 3)
	General disorders and administration site conditions - Other (superficial edema)		General disorders and administration site conditions - Other (superficial edema) (Gr 2)
INFECTIONS AND INFESTATIONS			

	Infection ^d		Infection^d (Gr 4)
INVESTIGATIONS			
	Alanine aminotransferase increased		Alanine aminotransferase increased (Gr 4)
	Alkaline phosphatase increased		Alkaline phosphatase increased (Gr 2)
	Aspartate aminotransferase increased		Aspartate aminotransferase increased (Gr 3)
	Blood bilirubin increased		Blood bilirubin increased (Gr 4)
	Creatinine increased		
	Lymphocyte count decreased		
Neutrophil count decreased			Neutrophil count decreased (Gr 4)
	Platelet count decreased		Platelet count decreased (Gr 3)
	Weight gain		Weight gain (Gr 2)
White blood cell decreased			White blood cell decreased (Gr 4)
METABOLISM AND NUTRITION DISORDERS			
	Anorexia		Anorexia (Gr 3)
	Dehydration		Dehydration (Gr 3)
	Hypokalemia		Hypokalemia (Gr 3)
	Hyponatremia		Hyponatremia (Gr 3)
	Hypophosphatemia		Hypophosphatemia (Gr 3)
MUSCULOSKELETAL AND CONNECTIVE TISSUE DISORDERS			
	Arthralgia		Arthralgia (Gr 2)
	Arthritis		Arthritis (Gr 2)
	Musculoskeletal and connective tissue disorder - Other (muscle cramps)		Musculoskeletal and connective tissue disorder - Other (muscle cramps) (Gr 2)
Myalgia			Myalgia (Gr 2)
NERVOUS SYSTEM DISORDERS			
	Dizziness		
	Headache		Headache (Gr 3)
RESPIRATORY, THORACIC AND MEDIASTINAL DISORDERS			
	Cough		
	Dyspnea		
	Laryngeal mucositis		Laryngeal mucositis (Gr 2)
	Pharyngeal mucositis		Pharyngeal mucositis (Gr 2)
	Pleural effusion		Pleural effusion (Gr 3)
	Pleuritic pain		
	Tracheal mucositis		Tracheal mucositis (Gr 2)
SKIN AND SUBCUTANEOUS TISSUE DISORDERS			
	Alopecia		
	Erythema multiforme		Erythema multiforme (Gr 2)
	Hyperhidrosis		
	Pruritus		Pruritus (Gr 2)
Rash maculo-papular			Rash maculo-papular (Gr 3)
	Skin hyperpigmentation		Skin hyperpigmentation (Gr 2)
	Skin hypopigmentation		Skin hypopigmentation (Gr 2)
VASCULAR DISORDERS			
	Vascular disorders - Other (Intra-tumoral hemorrhage)		Vascular disorders - Other (Intra-tumoral hemorrhage) (Gr 2)
	Vascular disorders - Other (Hemorrhage with thrombocytopenia)		Vascular disorders - Other (Hemorrhage with thrombocytopenia) (Gr 2)

¹This table will be updated as the toxicity profile of the agent is revised. Updates will be distributed to all Principal Investigators at the time of revision. The current version can be obtained by contacting [contact]. Your name, the name of the investigator, the protocol and the agent should be included in the e-mail.

²Gastrointestinal hemorrhage includes Anal hemorrhage, Cecal hemorrhage, Colonic hemorrhage, Duodenal hemorrhage, Esophageal hemorrhage, Esophageal varices hemorrhage, Gastric hemorrhage, Hemorrhoidal hemorrhage, Ileal hemorrhage, Intra-abdominal hemorrhage, Jejunal hemorrhage, Lower gastrointestinal hemorrhage, Oral hemorrhage, Pancreatic hemorrhage, Rectal hemorrhage, Retroperitoneal hemorrhage, and Upper gastrointestinal hemorrhage under the GASTROINTESTINAL DISORDERS SOC.

³Infection includes all 75 sites of infection under the INFECTIONS AND INFESTATIONS SOC.

⁴Gastrointestinal ulcer includes Anal ulcer, Colonic ulcer, Duodenal ulcer, Esophageal ulcer, Gastric ulcer, Ileal ulcer, Jejunal ulcer, Rectal ulcer, and Small intestine ulcer under the GASTROINTESTINAL DISORDERS SOC.

⁵Respiratory hemorrhage includes Bronchopulmonary hemorrhage, Epistaxis, Laryngeal hemorrhage, Mediastinal hemorrhage, Pharyngeal hemorrhage, and Pleural hemorrhage under the RESPIRATORY, THORACIC AND MEDIASTINAL DISORDERS SOC.

Also reported on Imatinib Mesylate (STI571) trials but with the relationship to Imatinib Mesylate (STI571) still undetermined:

BLOOD AND LYMPHATIC SYSTEM DISORDERS - Disseminated intravascular coagulation; Febrile neutropenia

CARDIAC DISORDERS - Cardiac arrest; Heart failure; Myocardial infarction; Ventricular arrhythmia

ENDOCRINE DISORDERS - Hypothyroidism

EYE DISORDERS - Blurred vision; Conjunctivitis; Papilledema; Photophobia; Watering eyes

GASTROINTESTINAL DISORDERS - Abdominal distension; Duodenal perforation; Esophageal fistula; Esophagitis; Gastritis; Gastrointestinal ulcer⁴; Ileus; Pancreatitis

GENERAL DISORDERS AND ADMINISTRATION SITE CONDITIONS - Flu like symptoms; General disorders and administration site conditions - Other (Guillain-Barre syndrome); Non-cardiac chest pain

HEPATOBIILIARY DISORDERS - Hepatic failure

IMMUNE SYSTEM DISORDERS - Allergic reaction; Autoimmune disorder

INVESTIGATIONS - CPK increased; GGT increased; Lipase increased; Weight loss

METABOLISM AND NUTRITION DISORDERS - Hypercalcemia; Hyperglycemia; Hypoalbuminemia; Hypocalcemia; Hypoglycemia; Hypomagnesemia

MUSCULOSKELETAL AND CONNECTIVE TISSUE DISORDERS - Avascular necrosis; Back pain; Bone pain; Generalized muscle weakness; Pain in extremity

NERVOUS SYSTEM DISORDERS - Depressed level of consciousness; Dysgeusia;

Encephalopathy; Hydrocephalus; Intracranial hemorrhage; Ischemia cerebrovascular; Peripheral motor neuropathy; Peripheral sensory neuropathy; Seizure; Tremor

PSYCHIATRIC DISORDERS - Anxiety; Confusion; Depression; Insomnia

RENAL AND URINARY DISORDERS - Acute kidney injury; Hematuria; Proteinuria; Renal and urinary disorders - Other (kidney stones)

REPRODUCTIVE SYSTEM AND BREAST DISORDERS - Irregular menstruation

RESPIRATORY, THORACIC AND MEDIASTINAL DISORDERS - Adult respiratory distress syndrome; Allergic rhinitis; Hypoxia; Pharyngolaryngeal pain; Pneumonitis; Pulmonary hypertension; Respiratory hemorrhage⁵; Voice alteration

SKIN AND SUBCUTANEOUS TISSUE DISORDERS - Dry skin; Purpura

VASCULAR DISORDERS - Hypotension; Thromboembolic event; Vasculitis

Note: Imatinib Mesylate (STI571) in combination with other agents could cause an exacerbation of any adverse event currently known to be caused by the other agent, or the combination may result in events never previously associated with either agent.

In addition to the above, the investigators on this trial have found a case report in the literature of tinnitus occurring in a patient while receiving imatinib mesylate (53).

